### **11.3 Day 1 ( $\pm$ 2 days) of Cycle 2 and every cycle thereafter**

Subjects will self-administer their morning dose of tipifarnib with food prior to the following procedures:

- Record concomitant medications
- Assessment of AEs
- Record subject weight
- Assess ECOG performance status.
- Symptom based physical examination
- Perform urine or serum pregnancy test for females of child-bearing potential only
- Perform serum chemistry laboratory tests (AST, ALT, total bilirubin, creatinine, potassium and calcium). Subjects are not required to be fasting. If clinically indicated, serum chemistry tests may be repeated more frequently.
- Perform hematology tests (hemoglobin, platelets, WBCs, neutrophils, neutrophil precursors, lymphocytes, monocytes and blasts). If clinically indicated, hematology tests may be repeated more frequently.

- Record any RBC, whole blood and platelet transfusions that were received since the last study visit.
- Conduct a drug accountability on the returned empty bottles and unused medications.

#### **11.4 Day 15 ( $\pm$ 2 days) of Cycle 1 and Cycle 2**

Subjects will self-administer their morning dose of tipifarnib with food prior to the following procedures:

- Record concomitant medications
- Assessment of AEs
- Symptom based physical examination
- Perform serum chemistry laboratory tests (AST, ALT, total bilirubin, creatinine, potassium and calcium). Subjects are not required to be fasting. If clinically indicated, serum chemistry tests may be repeated more frequently.
- Perform hematology tests (hemoglobin, platelets, WBCs, neutrophils, neutrophil precursors, lymphocytes, monocytes and blasts). If clinically indicated, hematology tests may be repeated more frequently.

#### **11.5 Day 25 ( $\pm$ 5 days) of Cycles 2, 4, 6, 9 and every approximately 12 weeks thereafter (Cycles 12, 15, etc.)**

The following procedures will be performed during the Day 25 visit. If the Day 25 visit coincides with a dosing day (e.g. visit occurs on Day 20, 21 or on Day 1 or 2 of the following cycle), subjects will self-administer their morning dose of tipifarnib with food prior to the procedures.

- Record concomitant medications
- Assessment of AEs
- Symptom based physical examination
- Perform hematology tests (hemoglobin, platelets, WBCs, neutrophils, neutrophil precursors, lymphocytes, monocytes and blasts)
- Perform bone marrow aspirate for disease and cytogenetic assessment during Cycles 2, 4, 6 and 9 only. A sample for biomarker analyses (PAXgene RNA tubes) will be taken at Cycle 2 only. Thereafter, bone marrow evaluations will occur as per institutional standard practice. If the bone marrow aspirate is inadequate for disease assessment, a bone marrow biopsy should be performed. If on this bone marrow sample, a CR or PR is observed, a bone marrow aspirate with cytogenetic assessment must be repeated 1 month later, i.e. prior to the end of the next cycle. Efforts should be made to document disease progression in subjects that discontinue treatment for reasons other than progression of disease.
- In MDS/MPN subjects, complete symptom assessment as per the MPN-SAF TSS

- Record any RBC, whole blood and platelet transfusions that were received since the last study visit.
- Collect serum and plasma samples for biomarker evaluation (Cycle 2 Day 25 visit only)

If the Day 25 visit coincides with a dosing day subjects will self-administer their evening dose of tipifarnib using the supplies provided by the study site.

## **11.6 End of Treatment Visit**

The following assessments will occur approximately 30 days ( $\pm$  7 days) after the last administration of study drug or immediately before the administration of another anticancer drug, whichever takes place first:

- Record concomitant medications
- Assessment of AEs
- Assess ECOG performance status
- Complete physical examination including vital signs (heart rate, blood pressure, temperature)
- Record subject weight
- Perform urine or serum pregnancy test for females of child-bearing potential only
- Perform serum chemistry laboratory tests (AST, ALT, total bilirubin, creatinine, potassium and calcium). Subjects are not required to be fasting.
- Perform hematology tests (hemoglobin, platelets, WBCs, neutrophils, neutrophil precursors, lymphocytes, monocytes and blasts)
- Perform coagulation tests (APTT, PT/INR)
- Perform bone marrow aspirate for disease, cytogenetic and biomarker assessment if in accordance with institutional standard practice. If the bone marrow aspirate is inadequate, a bone marrow biopsy should be performed. If on this bone marrow sample, a CR or PR is observed, a bone marrow aspirate with cytogenetic assessment must be repeated 1 month later.
- In MDS/MPN subjects, complete symptom assessment as per the MPN-SAF TSS
- Record any RBC, whole blood and platelet transfusions that were received since the last study visit.
- Blood sample for NGS oncogene panel sequencing
- Conduct drug accountability on the returned empty bottles and unused medications.

## **11.7 Post Treatment Follow up**

### **11.7.1 Follow-up Visit: Subjects who Terminate Treatment for Reasons other than Death or Disease Progression**

Subjects who terminated treatment for reasons other than death or disease progression will be assessed at regular intervals for disease progression and leukemic transformation.

The assessments to be conducted at each monthly visit are:

- Perform hematology tests (hemoglobin, platelets, WBCs, neutrophils, neutrophil precursors, lymphocytes, monocytes and blasts)

The assessments to be conducted at each approximately every 2 months through the first 6 months from the start of the subject's participation in this study and every approximately 12 weeks thereafter are:

- Perform bone marrow aspirate for disease assessment and cytogenetic assessment as part of the assessments conducted during the first 9 months from the start of the subject's participation in the study. Thereafter, bone marrow evaluations will occur during disease assessments in accordance with institutional standard practice. If the bone marrow aspirate is inadequate, a bone marrow biopsy should be performed. If on this bone marrow sample, a CR or PR is observed, a bone marrow aspirate with cytogenetic assessment must be repeated 1 month later.
- In MDS/MPN subjects, Complete symptom assessment as per the MPN-SAF TSS
- Record any RBC, whole blood and platelet transfusions that were received since the last study visit.

Assessments of AEs and concomitant medications may also be conducted if AEs were not resolved at the time of the End of Treatment visit.

### **11.7.2 Follow Up after Disease Progression**

Upon disease progression, all subjects in the study will be followed approximately every 12 weeks for survival and the use of subsequent therapy until either death or 12 months after accrual of the study cohort has been completed, whichever occurs first. Information on survival and subsequent anticancer therapy may be collected by phone.

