2. Day 25 visit ( $\pm$  5 days) should be performed during Cycles 2, 4, 6, 9 and every approximately 12 weeks thereafter (Cycles 12, 15, etc.) until disease progression.
3. An End of Treatment visit will be conducted within 30 days ( $\pm$  7 days) from the last dose of tipifarnib or immediately before the initiation of any other anticancer therapy.
4. Follow up visit required only for subjects who terminated treatment for reasons other than death or disease progression.
5. Information on subject's survival and use of subsequent anticancer therapy may be collected by phone. Upon disease progression, all subjects will be followed approximately every 12 weeks for survival and the use of subsequent therapy until either death or 12 months after accrual in the subject's study cohort has been completed, whichever occurs first.
6. Medical history is to include demographics, primary diagnosis and WHO classification, outcome and duration of response to prior cancer therapy and any ongoing AEs
7. Assessed throughout the course of the treatment and approximately 30 days after treatment discontinuation. Additional assessments may be performed until AE resolution or the AE is deemed irreversible by the Investigator.
8. Assessment to be performed within 14 days of Cycle 1 Day 1
9. In women with childbearing potential, pregnancy tests (urine or serum) will be conducted at screening (must be performed within 72 hours of Cycle 1 Day 1), on Day 1 of each treatment cycle beginning at Cycle 2 and at the End of Treatment visit. If a positive urine pregnancy test is obtained, a confirmatory serum pregnancy test should be conducted.
10. Assessment to be performed within 72 hours of Cycle 1 Day 1.
11. Assessment to be performed beginning at Cycle 2.

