### 6.2 Secondary Objectives and Endpoints

**Secondary Objective:** To assess the effect of tipifarnib on the following:

- Rate of CR, complete cytogenetic remission, partial remission, marrow response, and clinical benefit

- Duration of Response
- Rate of PFS at 1 year
- Rate of survival at 1 year
- AE profile according to NCI CTCAE v 4.03

**Secondary Endpoint:** Response assessments according to the MDS/MPN IWG criteria (MDS/MPN cohorts) or International Working Group criteria (AML cohorts); treatment emergent adverse events (TEAEs) and serious adverse events (SAEs) evaluated according to NCI CTCAE v.4.03.

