Subjects who terminate treatment for reasons other than death or disease progression will be assessed at regular intervals for disease progression (approximately every 2 months through the first 6 months from the start of the subject's participation in this study and every approximately 12 weeks thereafter) and leukemic transformation (monthly blood counts). Disease assessments performed during the first 9 months from the start of the subject's participation in the study will include bone marrow evaluation. Thereafter, bone marrow evaluations will occur during disease assessments in accordance with institutional standard practice. These assessments will continue until disease progression, withdrawal of subject's consent to study procedures or initiation of another anticancer therapy.

All subjects will be followed-up for safety during treatment and up to approximately 30 days ( $30 \pm 7$  days) after treatment discontinuation or until immediately before the initiation of another anticancer therapy, whichever occurs first. Additional follow up may be implemented until the subject recovers from any emergent treatment related toxicity or the AE is considered irreversible by the Investigator. Target organ toxicities will be monitored via clinical and laboratory assessments using the NCI CTCAE v.4.03 criteria.

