Determination of disease response in subjects with MDS/MPN will be performed by the Investigator according to the Myelodysplastic/Myeloproliferative International Working Group (MDS/MPN IWG criteria, Protocol Table 9). Similarly, disease progression will also be determined based on the MDS/MPN IWG criteria (Protocol Table 10). Determination of disease response in subjects with AML will be performed by the Investigator according to the International Working Group criteria (Cheson 2003). Similarly, disease progression will also be determined based on the IWG criteria (Cheson 2003).

Upon disease progression, all subjects in this study will be followed approximately every 12 weeks for survival and the use of subsequent therapy until either death or 12 months after accrual of the study cohort has been completed, whichever occurs first. Information on survival and subsequent anticancer therapy may be collected by phone.

Subjects who terminate treatment for reasons other than death or disease progression will be assessed at regular intervals for disease progression (approximately every 2 months through the first 6 months from the start of the subject's participation in this study and every approximately 12 weeks thereafter) and leukemic transformation (monthly blood counts). Disease assessments performed during the first 9 months from the start of the subject's

participation in the study will include bone marrow evaluation. Thereafter, bone marrow evaluations will occur during disease assessments in accordance with institutional standard practice. These assessments will continue until disease progression, withdrawal of subject's consent to study procedures or initiation of another anticancer therapy.

All subjects will be followed-up for safety during treatment and up to approximately 30 days (30 \pm 7 days) after treatment discontinuation or until immediately before the initiation of another anticancer therapy, whichever occurs first. Additional follow up may be implemented until the subject recovers from any emergent treatment related toxicity or the adverse event is considered irreversible by the Investigator. Target organ toxicities will be monitored via clinical and laboratory assessments using the NCI CTCAE v.4.03 criteria.

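### Scheduled survival contact starts only at disease progression, so a subject who starts another anticancer therapy without documented progression has none from that point, although 1-year survival is a secondary objective

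*Protocol*

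**What the plan says.** The protocol has two follow-up tracks after treatment.

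- **Off treatment without progression.** Table 1 footnote 4 reads: "Follow up visit required only for subjects who terminated treatment for reasons other than death or disease progression". These subjects have monthly blood counts and periodic disease assessments. Section 8.1 gives the stopping rule: "These assessments will continue until disease progression, withdrawal of subject's consent to study procedures or initiation of another anticancer therapy".
- **Survival contact.** Section 11.7.2 makes progression the trigger: "Upon disease progression, all subjects in the study will be followed approximately every 12 weeks for survival and the use of subsequent therapy". It runs "until either death or 12 months after accrual of the study cohort has been completed, whichever occurs first", and telephone collection is allowed. Table 1 footnote 5 ("Upon disease progression, all subjects will be followed approximately every 12 weeks for survival and the use of subsequent therapy") and SAP section 5.2 ("Upon disease progression, all subjects in this study will be followed approximately every 12 weeks for survival and the use of subsequent therapy") agree, as do the synopsis and section 8.1.

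Safety follow-up under section 8.1 lasts about 30 days "after treatment discontinuation or until immediately before the initiation of another anticancer therapy, whichever occurs first", with optional extension for unresolved related toxicity.

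"Rate of survival at 1 year" is listed in Protocol section 6.2 as a secondary objective. SAP section 10.3.4 counts all-cause deaths, censors other subjects at the last date known alive, and adds Cox hazard ratios and log-rank p-values by RAS status and by CXCR4/2 group.

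**The concern.** The two tracks do not meet. Take a subject who stops tipifarnib with stable disease, because of toxicity or lack of benefit, and then starts another therapy. The off-treatment assessments end at the new therapy. The survival contacts have not begun, because progression has not been documented, and it is no longer being looked for.

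The survival analysis needs data beyond that point. If the reason for changing therapy is related to prognosis (toxicity, failure to respond, or moving to a more intensive option), censoring near the change is informative. If changes are more frequent in one biomarker group, follow-up also differs between the groups that the hazard ratios compare.

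**Working it through.** **Step 1. Compare the rules for this subject.** The plan states no rate, power or sample size for 1-year survival, so there is no figure to reproduce.

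| Activity | Starts | Ends | After a switch without progression |
|---|---|---|---|
| Off-treatment assessments (8.1, 11.7.1) | Stopping without progression | Progression, withdrawal from procedures, or new therapy | Ended |
| Safety follow-up (8.1, 10.9) | Treatment | About 30 days after it, or new therapy | Ended, apart from follow-up of unresolved related events |
| Survival contact (11.7.2, Table 1 footnote 5, SAP 5.2) | Progression | Death, or 12 months after cohort accrual | Not started |

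In Table 1, survival information is marked only under the follow-up contact column, which footnote 5 ties to progression.

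**Step 2. Do the documents expect such subjects?** Yes. SAP sections 10.3.2 and 10.3.3 censor duration of response and PFS at the last assessment before subsequent therapy. Those rules matter only if therapy can change before progression. SAP section 8 also lists non-progression reasons for stopping treatment.

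**Step 3. What does the survival analysis do with them?** SAP section 10.3.4 has no censoring rule at new therapy. The last-known-alive date comes from vital signs, laboratory, disease assessment, death, study discontinuation and end-of-study forms. The survival contact is not named. Unless one of the last three forms carries a later date, the subject is censored at about the switch.

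**Step 4. Illustrate the size.** Every rate here is an assumption.

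*Simple mixture.* A fraction f switches very early, the others have 1-year survival 0.50, and switchers have survival s. Kaplan-Meier stays near 0.50, while true survival = (1 − f) × 0.50 + f × s.

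- s = 0.30: f = 0.1, 0.2, 0.3 gives 0.48, 0.46, 0.44. The estimate is 2, 4 or 6 points too high.
- s = 0.60: the same f gives 0.51, 0.52, 0.53. The estimate is 1, 2 or 3 points too low.

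In an 18-subject cohort, f = 0.1 to 0.3 is 1.8 to 5.4 subjects, about 2 to 5.

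*Switching spread over the year.* Let the death hazard be λ = −ln(0.50) = 0.693 per year. Let switching have constant hazard c, chosen so that c/(λ + c) × [1 − exp(−(λ + c))] = f. For f = 0.20, c = 0.318. After switching, the death hazard is rλ. Kaplan-Meier estimates exp(−λ) = 0.500, whereas

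true survival = exp(−(λ + c)) + ∫₀¹ c·exp(−(λ + c)u)·exp(−rλ(1 − u)) du.

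For f = 0.20 the first term is exp(−1.011) = 0.364.

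| r | Integral | True 1-year survival | Kaplan-Meier minus true |
|---|---|---|---|
| 0.5 | 0.164 | 0.528 | −2.8 points |
| 1 | 0.136 | 0.500 | 0 |
| 2 | 0.096 | 0.460 | +4.0 points |
| 3 | 0.071 | 0.435 | +6.5 points |

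Over f = 10–30%, 1-year survival 0.40–0.60 and r = 0.5–3, the difference runs from about −5 to +10 points.

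*Precision.* With n = 18 and complete follow-up, SE = √(0.50 × 0.50/18) = 0.118. With f = 0.20, the asymptotic Greenwood SE = 0.50 × √{λ[exp(λ + c) − 1]/[(λ + c) × 18]} = 0.129.

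**The case against.** A reader might infer that these subjects have no follow-up at all. The documents do not support that. Deaths can reach the database through the death, discontinuation or end-of-study forms, and related adverse events are followed to stabilisation under section 10.12. Nor does contact necessarily end at the End of Treatment visit: someone who switches later has monthly counts and periodic assessments until the new therapy begins. What is missing is scheduled survival contact from the switch onward.

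Two provisions reduce the number affected. Section 11.5 asks for efforts to document progression after discontinuation for other reasons. A disease assessment is also planned at End of Treatment, before any new anticancer drug, and progression found there does start survival follow-up. Neither sets a survival contact for a subject in whom progression is not found. The reference to all subjects in section 11.7.2 does not help, because the same sentence makes progression the condition.

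Section 9.12 overlaps with this point. It bars other anticancer therapy during the study and withdraws a subject who needs a non-permitted drug. A correction there that kept such subjects in survival follow-up would close part of the gap, so the two changes belong together.

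The size argument largely stands. No rate used above comes from the documents. The simple mixture censors switchers almost at time zero, which overstates the effect: efficacy uses the per-protocol set, which requires a post-baseline assessment, and the first one scheduled on treatment is Cycle 2 Day 25. One-year survival carries no hypothesis, power or decision rule.

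**Conclusion.** The gap is real and follows from the text. A subject who starts another therapy without documented progression has no scheduled survival contact from then on, while the survival analysis counts all-cause deaths beyond that point. Such subjects are likely to be censored at about the switch, and that may be informative.

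The size and direction are unknown. On assumed values the bias is mostly a few points either way. It is zero if switchers have the same hazard, and then only precision is lost. At 50% survival and 20% switching it runs from −2.8 to +6.5 points, against a standard error of 12 to 13 points with 18 subjects. Even the +10-point extreme is below one standard error.

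A reader might infer that the published survival rate will be biased upward, or that the CXCR4/2 comparison is compromised. Neither is shown: the first depends on unknown prognosis after switching, and the second also on how switching differs between groups. Cohort success rests on response rate alone and is unaffected. This is a modest weakness in a secondary endpoint, worth correcting because the outcomes are obtainable cheaply.

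**What to change.** 1. In the Protocol synopsis, Table 1 footnote 5, sections 8.1 and 11.7.2, and SAP section 5.2, start the 12-weekly survival contact at documented progression or the start of another anticancer treatment, whichever is earlier. Keep the existing end of follow-up.
2. Apply this to everyone who has not withdrawn consent to survival follow-up. State that withdrawing from study procedures alone does not end it, and record the two separately.
3. Reconcile the new sentence with the study-withdrawal wording in section 9.12; otherwise the two will conflict.
4. Name the survival contact as a source for the last-known-alive date in SAP section 10.3.4.
5. If follow-up is already advanced, seek vital status for affected subjects where consent allows, and report how many were censored at a therapy change, by biomarker group.

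The cost is a short text change in both documents and a few telephone contacts per affected subject, a method already permitted. No visit, procedure or treatment rule is added.

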## **12 STATISTICAL METHODS**

### **12.1 Populations**

#### **12.1.1 Efficacy Analysis**

The primary population for the efficacy analysis is the Per Protocol analysis set (PPS) that includes subjects who received at least one dose of tipifarnib, and have a baseline disease assessment and at least one post baseline disease assessment. Subjects who do not receive at

[figure not shown]
least one dose of tipifarnib will be replaced. Subjects who do not have at least one post baseline disease assessment may be replaced.

[figure not shown]
### **12.1.2 Safety Analysis**

The primary population for the safety analysis is the Full Analysis Set (FAS), defined as all subjects who received at least one dose of tipifarnib in this study.

## **12.2 Endpoints**

### **12.2.1 Efficacy**

The efficacy objectives and endpoints are listed in section 6. Response assessment in the MDS/MPN cohorts will be conducted according to the MDS/MPN IWG criteria ([Table 9](#) and [Table 10](#)). Response assessments in the AML cohorts will be conducted according to the International Working Group criteria (Cheson 2003). 

 Additional categories of response may be defined and assessed based on the observed data during exploratory analyses.

### **12.2.2 Safety and Tolerability**

#### **12.2.2.1 Patient Adherence**

Number of treatment cycles per patient will be summarized by numbers and percents of subjects who received each number of treatment cycles.

